Propensity scores will be calculated using a multivariable logistic regression model with the dependent outcome as treatment initiation with prasugrel (versus clopidogrel). In addition to age, and gender, this model will include all baseline covariates demonstrating significant differences ($p < 0.05$) between groups. Additional variables for which there is consensus that may be related to either the outcome or exposure will also be included as covariates, even in the absence of significant baseline differences between groups. From this logistic regression model, each observation will be assigned a predicted probability for prasugrel treatment. Baseline characteristics including calculated propensity score will be reviewed to better understand the data and specified analyses plan for the outcomes (stratification, matching, IPW, and etc) will be finalized and documented prior to any actual analyses on the outcomes. The distribution of propensity scores for the entire cohort and each treatment group will be visually examined. Mutually exclusive strata will then be generated based on the propensity scores for the entire cohort, a process which will be blinded to any outcome data in order to avoid bias in selection. The number of strata and their respective cut-points will not be defined *a priori* but will be based on fulfilling the following criteria:

1. Sufficient number of strata to ensure adequate bias adjustment (i.e. at least 5 strata) [Rosenbaum et al., 1984];
2. Sufficient proportion of prasugrel and clopidogrel patients (at least 3%) within each stratum to allow reliable risk estimation [D'Agostino et al., circulation 2007];
3. Adequate balance in baseline covariates will be assessed by calculating the standardized differences between exposure groups within strata for the following variables: age, gender, serum creatinine, serum hemoglobin and prevalence of DM. A standardized difference exceeding 10% will be considered as inadequate bias adjustment..
4. Individuals with an extremely high or low propensity for prasugrel, defined as propensity scores exceeding the 95th or below the 5th percentile for the

entire cohort, may be removed from the analysis of the primary MACE endpoint (i.e. trimming).

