8.1 Demographic and Baseline Variables

For each center the variables listed in the table in the section 12 Listing of Tables, Listings, and Figures will be considered as demographic or baseline variables.

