Min , Max	x.xx,x.xx	x.xx,x.xx	x.xx,x.xx	
Ethnicity		xx (x.x%)	xx (x.x%)	x.xxx
Hispanic	xx (x.x%)	xx (x.x%)	xx (x.x%)	
Non-Hispanic	xx (x.x%)	xx (x.x%)	xx (x.x%)	
Race				
African American	xx (x.x%)	xx (x.x%)	xx (x.x%)	x.xxx
White	xx (x.x%)	xx (x.x%)	xx (x.x%)	x.xxx
Other	xx (x.x%)	xx (x.x%)	xx (x.x%)	x.xxx
Diabetes at baseline	xx (x.x%)	xx (x.x%)	xx (x.x%)	x.xxx
Insulin-requiring diabetes at baseline	xx (x.x%)	xx (x.x%)	xx (x.x%)	x.xxx
Hypertension	xx (x.x%)	xx (x.x%)	xx (x.x%)	x.xxx
Hypercholesterolemia	xx (x.x%)	xx (x.x%)	xx (x.x%)	x.xxx
Pre-Procedure Creatinine, mg/dl				x.xxx
N, N Missing	xxx,x	xxx,x	xxx,x	
Mean ± Std	x.xx ± x.xx	x.xx ± x.xx	x.xx ± x.xx	
Median	x.xx	x.xx	x.xx	
Min , Max	x.xx,x.xx	x.xx,x.xx	x.xx,x.xx	
Pre-Procedure Hemoglobin, mg/dl				x.xxx
N, N Missing	xxx,x	xxx,x	xxx,x	

Table 1. Summary of Baseline Characteristics by Therapy at PCI.

	Overall (N = XX)	Prasugrel XX (XX%)	Clopidogrel XX (XX%)	Pvalue
Mean ± Std	x.xx ± x.xx	x.xx ± x.xx	x.xx ± x.xx	
Median	x.xx	x.xx	x.xx	
Min , Max	x.xx,x.xx	x.xx,x.xx	x.xx,x.xx	
Troponin				x.xxx
N, N Missing	xxx,x	xxx,x	xxx,x	
Mean ± Std	x.xx ± x.xx	x.xx ± x.xx	x.xx ± x.xx	
Median	x.xx	x.xx	x.xx	
Min , Max	x.xx,x.xx	x.xx,x.xx	x.xx,x.xx	
Baseline CK-MB, ng/ml				x.xxx
N, N Missing	xxx,x	xxx,x	xxx,x	
Mean ± Std	x.xx ± x.xx	x.xx ± x.xx	x.xx ± x.xx	
Median	x.xx	x.xx	x.xx	
Min , Max	x.xx,x.xx	x.xx,x.xx	x.xx,x.xx	
Peak serum creatinine, mg/dl				x.xxx
N, N Missing	xxx,x	xxx,x	xxx,x	
Mean ± Std	x.xx ± x.xx	x.xx ± x.xx	x.xx ± x.xx	
Median	x.xx	x.xx	x.xx	
Min , Max	x.xx,x.xx	x.xx,x.xx	x.xx,x.xx	
Nadir hemoglobin, g/dl (lowest within 72 hours)				x.xxx
N, N Missing	xxx,x	xxx,x	xxx,x	
Mean ± Std	x.xx ± x.xx	x.xx ± x.xx	x.xx ± x.xx	
Median	x.xx	x.xx	x.xx	
Min , Max	x.xx,x.xx	x.xx,x.xx	x.xx,x.xx	
Peak CK-MB, ng/ml (highest 6-24 hours after PCI)				x.xxx
N, N Missing	xxx,x	xxx,x	xxx,x	
Mean ± Std	x.xx ± x.xx	x.xx ± x.xx	x.xx ± x.xx	
Median	x.xx	x.xx	x.xx	
Min , Max	x.xx,x.xx	x.xx,x.xx	x.xx,x.xx	
Peak Troponin (highest 6-24 hours after PCI)				x.xxx
N, N Missing	xxx,x	xxx,x	xxx,x	
Mean ± Std	x.xx ± x.xx	x.xx ± x.xx	x.xx ± x.xx	
Median	x.xx	x.xx	x.xx	
Min , Max	x.xx,x.xx	x.xx,x.xx	x.xx,x.xx	
Smoking	xx (x.x%)	xx (x.x%)	xx (x.x%)	x.xxx
ISCHEMIC HISTORY				
Family history of CAD	xx (x.x%)	xx (x.x%)	xx (x.x%)	x.xxx
Previous MI	xx (x.x%)	xx (x.x%)	xx (x.x%)	x.xxx
Previous PCI	xx (x.x%)	xx (x.x%)	xx (x.x%)	x.xxx

Table 1. Summary of Baseline Characteristics by Therapy at PCI.

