	Overall (N = XX)	Prasugrel XX (XX%)	Clopidogrel XX (XX%)	Pvalue
Previous CABG	xx (x.x%)	xx (x.x%)	xx (x.x%)	x.xxx
Prior CHF	xx (x.x%)	xx (x.x%)	xx (x.x%)	x.xxx
Prior PAD	xx (x.x%)	xx (x.x%)	xx (x.x%)	x.xxx
Prior Cerebrovascular Disease	xx (x.x%)	xx (x.x%)	xx (x.x%)	x.xxx
Left ventricular ejection fraction (%)				x.xxx
N, N Missing	xxx,x	xxx,x	xxx,x	
Mean ± Std	x.xx ± x.xx	x.xx ± x.xx	x.xx ± x.xx	
Median	x.xx	x.xx	x.xx	
Min , Max	x.xx,x.xx	x.xx,x.xx	x.xx,x.xx	
CAD Presentation	xx (x.x%)	xx (x.x%)	xx (x.x%)	x.xxx
Non-ST-elevation myocardial infarction	xx (x.x%)	xx (x.x%)	xx (x.x%)	
ST-elevation myocardial infarction	xx (x.x%)	xx (x.x%)	xx (x.x%)	
Unstable Angina	xx (x.x%)	xx (x.x%)	xx (x.x%)	
PCI status	xx (x.x%)	xx (x.x%)	xx (x.x%)	x.xxx
PCI Indication	xx (x.x%)	xx (x.x%)	xx (x.x%)	x.xxx
Stress or Imaging pre procedure	xx (x.x%)	xx (x.x%)	xx (x.x%)	x.xxx
MEDICATIONS AT ADMISSION				
Beta Blocker	xx (x.x%)	xx (x.x%)	xx (x.x%)	x.xxx
Ca Channel Blocker	xx (x.x%)	xx (x.x%)	xx (x.x%)	x.xxx
Aspirin	xx (x.x%)	xx (x.x%)	xx (x.x%)	x.xxx
Clopidogrel	xx (x.x%)	xx (x.x%)	xx (x.x%)	x.xxx
Prasugrel	xx (x.x%)	xx (x.x%)	xx (x.x%)	x.xxx
Ticagrelor	xx (x.x%)	xx (x.x%)	xx (x.x%)	x.xxx
Nitrate	xx (x.x%)	xx (x.x%)	xx (x.x%)	x.xxx
Ranexa	xx (x.x%)	xx (x.x%)	xx (x.x%)	x.xxx
MEDICATIONS AT DISCHARGE				
ACE-I or ARB	xx (x.x%)	xx (x.x%)	xx (x.x%)	x.xxx
Aspirin	xx (x.x%)	xx (x.x%)	xx (x.x%)	x.xxx
Beta Blocker	xx (x.x%)	xx (x.x%)	xx (x.x%)	x.xxx
Statin	xx (x.x%)	xx (x.x%)	xx (x.x%)	x.xxx
Clopidogrel	xx (x.x%)	xx (x.x%)	xx (x.x%)	x.xxx
75 mg	xx (x.x%)	xx (x.x%)	xx (x.x%)	x.xxx
150 mg	xx (x.x%)	xx (x.x%)	xx (x.x%)	x.xxx
Prasugrel	xx (x.x%)	xx (x.x%)	xx (x.x%)	x.xxx
5 mg	xx (x.x%)	xx (x.x%)	xx (x.x%)	x.xxx
10 mg	xx (x.x%)	xx (x.x%)	xx (x.x%)	x.xxx
Anticoagulant	xx (x.x%)	xx (x.x%)	xx (x.x%)	x.xxx

Table 2. Summary of Procedural Characteristics by Discharge Therapy.

	Overall (N = XX)	Prasugrel XX (XX%)	Clopidogrel XX (XX%)	Pvalue
PROCEDURAL MEDICATIONS				
Aspirin	xx (x.x%)	xx (x.x%)	xx (x.x%)	x.xxx
Fondaparinux	xx (x.x%)	xx (x.x%)	xx (x.x%)	x.xxx
LMWH	xx (x.x%)	xx (x.x%)	xx (x.x%)	x.xxx
UFH	xx (x.x%)	xx (x.x%)	xx (x.x%)	x.xxx
Bivalirudin	xx (x.x%)	xx (x.x%)	xx (x.x%)	x.xxx
IIb/IIIa	xx (x.x%)	xx (x.x%)	xx (x.x%)	x.xxx
Clopidogrel	xx (x.x%)	xx (x.x%)	xx (x.x%)	x.xxx
Prasugrel	xx (x.x%)	xx (x.x%)	xx (x.x%)	x.xxx
ANGIOGRAPHIC CHARACTERISTICS				
Multivessel disease	xx (x.x%)	xx (x.x%)	xx (x.x%)	x.xxx
Total stent length				x.xxx
N, N Missing	xxx,x	xxx,x	xxx,x	

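### SAP Table 1 labels post-PCI values as baseline, and the p<0.05 rule in SAP 6.1 does not keep them out of the adjustment models

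*SAP*

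**What the plan says.** SAP 6.1 defines exposure by the drug received at the time of PCI, regardless of the drug at discharge.

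Table 1 in SAP section 12 is titled as a summary of baseline characteristics and gives a between-group p-value for its variables. Beside the pre-procedure laboratory values it lists "Nadir hemoglobin, g/dl (lowest within 72 hours"), peak serum creatinine, "Peak CK-MB, ng/ml (highest 6-24 hours after PCI") and peak troponin over the same 6-24 hours. It also has a block headed "MEDICATIONS AT DISCHARGE".

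SAP 8.1 says that the variables in the section 12 table "will be considered as demographic or baseline variables".

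On the propensity model, SAP 6.1 says: "In addition to age, and gender, this model will include all baseline covariates demonstrating significant differences", with the threshold at p<0.05. The covariate-adjusted Cox model (sensitivity analysis 1) uses the same rule. Secondary clinical outcomes, which under SAP 4.2 include in- and out-of-hospital bleeding from index PCI, use the same propensity stratification, with covariate adjustment as a sensitivity analysis.

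SAP 6.1 also provides that baseline characteristics and the propensity score are reviewed, and that the analysis plan "will be finalized and documented prior to any actual analyses on the outcomes".

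**The concern.** A propensity score should contain what was known when treatment was chosen. A value that treatment can change, or that records the outcome itself, does not belong in it. Read in sequence, Table 1, SAP 8.1 and the p<0.05 rule admit such values, and no sentence limits the rule to pre-procedure data.

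- **Bleeding.** An early bleed lowers the nadir hemoglobin. The nadir window is 72 hours, the same length as that of the post-procedure bleeding field in Attachment 1. Balancing the groups on the nadir therefore balances away part of the effect being estimated.
- **MACE, through biomarkers.** Peak CK-MB and troponin come from the 6-24 hour window that Attachment 1 prefers for diagnosing post-procedure MI. SAP 6.1 counts index-hospital events in primary MACE, although the note to Table 4 speaks of hospitalization for MI.
- **MACE, through discharge drugs.** A patient who dies in hospital has no discharge prescriptions. If those fields are coded 'no', they mark the deaths. The primary analysis keeps in-hospital deaths; only sensitivity analysis 5 removes them.

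**Working it through.** The plan gives no figure on this point. The only number borrowed from it is 4,303 per group (SAP 6.8), taken as given. Every clinical rate below is an assumption.

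**1. How small a difference triggers entry.** The smallest standardized difference with p<0.05 is 1.96 × √(2/n).
- n = 4,303: 1.96 × √(2/4303) = 0.042, or 4.2%. With 10% fewer patients (3,873) it is 4.5%. The SAP's own limit for inadequate balance is 10%.
- Nadir hemoglobin with SD 1.5 to 2.2 g/dl: 0.0423 × 1.5 = 0.06 to 0.0423 × 2.2 = 0.09 g/dl.
- A drug that 90% receive: 1.96 × √(2 × 0.9 × 0.1/4303) = 1.3 percentage points.
- The chance of entry is 79% at a true standardized difference of 0.06, 96% at 0.08 and 99.6% at 0.10.

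SAP 6.3 expects significant group differences, so entry is plausible.

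**2. Nadir hemoglobin and 90-day bleeding.** The simulation used a logistic propensity score, 5 or 10 strata and a stratified Cox model. It had one measured confounder; center and missing data were not modelled. Assumptions:
- pre-procedure hemoglobin mean 14, SD 1.7, group difference -0.2, 0 or +0.2 g/dl;
- in-hospital bleeding 3-6%, of which 35% major (mean fall 3.5 g/dl; other bleeds 1 g/dl);
- later bleeding 1.5-3%.

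| True HR | Without nadir | With nadir |
|---|---|---|
| 1.5 | 1.47-1.52 | 1.38-1.48 |
| 1.2 | 1.17-1.21 | 1.14-1.19 |

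The loss is 3-21% of the log hazard ratio. With no drug effect, both models read 0.98-1.01. Entry is 5-22% likely if pre-procedure hemoglobin is equal, and at least 93% likely with a 0.2 g/dl difference. If only the nadir enters and pre-procedure values are equal, the readings are 1.47-1.50 and 1.17-1.20, so almost nothing is lost.

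A second, simpler simulation used odds ratios, 10 strata, 4% bleeding risk and a bleed that lowers the nadir by 1.0-1.5 SD. It shows how far the size depends on one assumption: whether prasugrel also lowers the nadir apart from recorded bleeds.

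| Extra fall on prasugrel | True 1.4 reads | True 1.0 reads |
|---|---|---|
| none | 1.26-1.35 | 0.99-1.02 |
| 0.06 SD | 1.09-1.18 | 0.82-0.87 |
| 0.10 SD | 0.94-1.09 | 0.73-0.80 |
| 0.20 SD | 0.70-0.85 | 0.52-0.60 |

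With pre-procedure covariates only, the same data read 1.36-1.43 and 0.98-1.02.

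**3. Peak CK-MB and MACE.** With in-hospital MI at 1-3%, raising the peak 3- to 10-fold, the MACE hazard ratio changes by 0.000-0.023. Peak troponin and peak creatinine were not estimated.

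**4. Discharge drugs and MACE.** Assumptions: 8% control MACE; in-hospital death 0.5-2%; aspirin, statin, beta blocker and ACE-I/ARB given to 97, 90, 85 and 70% of survivors. The propensity-stratified hazard ratio is multiplied as follows.
- Deaths coded 0, use differing by 1-3 points among survivors (0.3 of that for aspirin): 1.01-1.12 if prasugrel patients get more of the drugs, 0.91-0.99 if fewer.
- Deaths coded 0, no difference among survivors: 1.00-1.02.
- Fields blank and imputed: 1.00.

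**The case against.** The strongest reply is that no competent analyst would enter these values and that the SAP does not clearly tell them to.

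- SAP 8.1 sits in a reporting section and gives no table number. Applied to all of section 12, it would make in-hospital events and costs baseline too, so it cannot be read mechanically.
- SAP 8.3 handles medications separately, by admission, discharge and procedure, without calling them baseline. Protocol 3.3.4 speaks of baseline characteristics and baseline treatment use.
- The covariates that 6.1 names are all pre-procedure or procedural, and Attachment 1 labels the creatinine and hemoglobin fields as pre-procedure.
- The nadir row does not say after PCI, and peak creatinine has no window.
- The review before outcome analysis could remove the offending rows.

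Much of this stands, and it is why entry is possible rather than certain. It does not close the gap. Table 1 is the table titled baseline, the rule in 6.1 says all, and the review carries no timing criterion. The nadir and peak rows stand apart from pre-procedure values, so the post-PCI reading is the natural one. The balance check covers only age, gender, creatinine, hemoglobin and diabetes, so it would not reveal the problem.

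A reader might infer more: that discharge drugs will bias the primary MACE hazard ratio by up to about 12%. The documents do not support that. The drugs would have to enter despite SAP 8.3, deaths would have to be coded 'no' (Attachment 1 gives no rule for patients who died), and use would have to differ among survivors. The simulated case also supposes that analysts drop discharge prasugrel and clopidogrel, which nearly determine exposure and would break the SAP's 3% stratum rule, yet keep the rest of the same block. Nothing in the SAP describes that.

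**Conclusion.** The point holds as a defect in the written rule: as it stands, the SAP allows adjustment for values that arise after PCI, and a 4.2% standardized difference is enough to bring one in.

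The clearest harm is to the secondary bleeding comparison. Its direction is understood: part of any bleeding effect is removed. Its size is not, since it runs from almost nothing to a reversal depending on how much prasugrel lowers the nadir apart from recorded bleeds. For primary MACE, the estimated biomarker effect is at most about 0.02 on the hazard ratio. The discharge-drug effect is conditional, and its size rests wholly on assumed rates. The SAP should be changed, but the point does not show that the primary result would be wrong.

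**What to change.** In SAP 6.1, state that the propensity and covariate models use only:
- variables recorded before the index PCI (demographics, history, presentation, admission medications, pre-procedure laboratory values);
- the index-procedure variables in Table 2, other than the P2Y12 drugs that define exposure;
- the variables already named in 6.1.

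State also that nadir hemoglobin, peak creatinine, peak CK-MB, peak troponin and all discharge medications are excluded whatever their p-value. Limit 'baseline' in SAP 8.1 to match. Move the excluded rows to a separate descriptive post-procedure table, with discharge drugs shown for patients discharged alive.

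The index PCI is the workable cut-off because Attachment 1 dates the PCI but records loading only as yes or no, so timing relative to the first dose cannot be checked. Keeping the Table 2 variables retains control for lesion complexity, stent length and target vessel.

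The cost is a few sentences and a rearranged table, with no new data. The one real loss is that peak biomarkers also reflect index infarct size, so some control for severity is given up. Pre-procedure troponin and CK-MB, CAD presentation and LVEF remain available.

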3.4.2. Economic Outcomes Analyses

3.4.2.1. Unadjusted Outcomes Analyses

Data will be gathered on all patients in the study concerning their index and follow-up hospitalizations for MI, stroke, repeat unplanned coronary revascularization and stent thrombosis. The frequency of PCI and/or coronary artery bypass graft (CABG) procedures during these hospitalizations will be captured. The proportion of patients with follow-up hospitalization for these diagnoses will be compared between prasugrel and clopidogrel groups using Chi-square tests. The crude unadjusted rates will be calculated for each group using the Kaplan-Meier method and compared using the log-rank test.

All hospitalizations (except for bleeding-related hospitalizations) will be assigned a DRG based on the diagnoses of interest without knowledge of the patient's treatment assignment. The DRGs will be converted to direct medical costs for hospitalization based on Medicare Part A reimbursement. Bleeding-related rehospitalization costs will not be included in this specific analysis as the specific DRG related to this type of admission cannot be determined in this dataset. An additional cost for physicians will be estimated using the Resource-Based Relative

Value Scale (RBRVS) and the Medicare payment schedule. When a hospitalization includes more than 1 event, the highest paying DRG will be used.

Total direct medical costs for the index hospitalization and subsequent hospitalizations will be totaled. Indirect costs (lost productivity) due to premature CV death will be calculated. Hospital length of stay will be calculated as the number of days from hospital admission to discharge. The difference in mean costs (direct and indirect), length of stay, and other continuous resource utilization outcomes (for example, counts of CV-related hospitalizations per patient) between treatment groups will be calculated using t-tests. Exact tests, bootstrapping and/or nonparametric tests will be used as appropriate.

In Study B020, clinical outcomes are measured by days from index hospital admission whereas health economic outcomes are measured by days from index hospital discharge.

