Results from TRITON-TIMI 38 established the superior efficacy of prasugrel in combination with aspirin over clopidogrel plus aspirin in reducing ischemic events in ACS patients managed with PCI (Wiviott et al. 2007). Compared with clopidogrel, prasugrel caused higher rates of major bleeding, particularly in patients with advanced age, low body weight, previous stroke or transient ischemic attack. Since its United States (US) approval in 2009, there are few observational studies that directly compare outcomes between prasugrel and clopidogrel for ischemic and bleeding events. The TRANSLATE-ACS registry was a prospective observational study of approximately 12,000 patients with myocardial infarction ([MI], ST-segment elevation myocardial infarction [STEMI] or non-ST-segment elevation myocardial infarction [NSTEMI]) managed with PCI (Chin et al. 2011). The study evaluated the comparative effectiveness and safety of prasugrel compared with clopidogrel in the usual care environment (Wang et al. 2014). However, as long-term follow-up was prospectively collected, patient informed consent was required that limited the ability to collect data on all MI patients managed with a PCI. Therefore, there are a large number of eligible patients who were not included in the TRANSLATE-ACS database because they either did not give consent or were discharged prior to being identified and consent obtained.

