6.1 Methods

Primary Objective

The exposure groups for the primary analysis will be defined as those patients receiving prasugrel or clopidogrel at the time of PCI (i.e. loaded peri-procedurally or currently taking in the absence of a load). All patients will be assigned to one of these mutually exclusive groups irrespective of medication administered at discharge. Patients administered both medications at the time of PCI will be excluded for any comparative analyses of treatments.

For descriptive purposes, baseline clinical (including laboratory evaluations) and demographic and procedural characteristics will be compared between groups using student's t-test and chi-square test or Fisher's exact test for continuous and categorical variables, respectively.

In-hospital (that is, post-procedural) outcomes will be assessed by comparing the proportion of post-procedural events between prasugrel and clopidogrel groups. These crude unadjusted binary proportions will be performed using a Chi-square test between groups.

The primary endpoint of interest is the first occurrence of MACE within 90 days from date of index PCI. For purposes of this primary analysis, event-free patients will be censored at 90 days or last contact, whichever comes first. For the primary outcome of interest, the crude unadjusted 90-day rates of MACE will be calculated for each group using the *Kaplan-Meier method, also including index hospital events*. Crude rates will be compared between groups using the logrank test (Kalbfleisch et al. 1980; Prentice et al. 1978).

To evaluate the adjusted associations between treatment group (therapy initiation with prasugrel versus clopidogrel) and the primary MACE outcome, hazard ratios will be calculated using Cox proportional hazards regression that are stratified by the propensity to receive either prasugrel or clopidogrel.

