The following tables will be used to derive from an accompanying data set or spreadsheet that will be used to automate the aesthetic aspects of table production.

Table Listings

Number	Table Title	Summary Statistics	Formal Analysis
1	Summary of Baseline Characteristics by therapy at PCI	n, mean, SD, Median, min, max, n (%)	χ^2 test or Fisher's exact test will be performed for categorical variables as necessary and independent sample t-test continuous variables
2	Summary of Procedural Characteristics by therapy at PCI	n, mean, SD, Median, min, max, n (%)	χ^2 test or Fisher's exact test will be performed for categorical variables as necessary and independent sample t-test continuous variables
3	Procedural Events	n (%)	χ^2 test test for proportion
4	Clinical Outcomes by therapy at PCI	KM estimation [95% CI], crude HR, Propensity-adjusted HR; Covariate-adjusted HR	log-rank test, Cox model
5	Economic Outcomes by Discharge Therapy	mean, SD, Median, min, max, 95% CI for continuous variables, n (%)	t-tests, exact tests, and/or nonparametric tests; bootstrapping; GLM for continuous variables
		KM estimation [95% CI], crude HR, HR propensity score adjusted	χ^2 test, fishers exact test, KM estimation, log rank test, Cox model for categorical variables

Figure Listings

	Title	outcome	Pop	Type of graph	Horizontal Variables	Vertical Variables	Groupings	Statistics	Facets
1	KM rates at 90 days	MACE	Full Analysis	KM	time	probability		KM Estimates	NA
1a	KM rates by Therapy at PCI at 90 days	MACE	Full Analysis	KM	time	probability	Treatment	KM Estimates	NA
2	KM rates at 1 year	MACE	Full Analysis	KM	time	probability		KM Estimates	NA
2a	KM rates by Therapy at PCI at 1 year	MACE	Full Analysis	KM	time	probability	Treatment	KM Estimates	NA

The corresponding Mock Tables are in the following section.

Table 1. Summary of Baseline Characteristics by Therapy at PCI.

	Overall (N = XX)	Prasugrel XX (XX%)	Clopidogrel XX (XX%)	Pvalue
DEMOGRAPHICS				
Age, years				x.xxx
N, N Missing	xxx,x	xxx,x	xxx,x	
Mean ± Std	x.xx ± x.xx	x.xx ± x.xx	x.xx ± x.xx	
Median	x.xx	x.xx	x.xx	
Min , Max	x.xx,x.xx	x.xx,x.xx	x.xx,x.xx	
Gender (female)	xx (x.x%)	xx (x.x%)	xx (x.x%)	x.xxx
Height (cm)				x.xxx
N, N Missing	xxx,x	xxx,x	xxx,x	
Mean ± Std	x.xx ± x.xx	x.xx ± x.xx	x.xx ± x.xx	
Median	x.xx	x.xx	x.xx	
Min , Max	x.xx,x.xx	x.xx,x.xx	x.xx,x.xx	
Weight (Kg)				x.xxx
N, N Missing	xxx,x	xxx,x	xxx,x	
Mean ± Std	x.xx ± x.xx	x.xx ± x.xx	x.xx ± x.xx	
Median	x.xx	x.xx	x.xx	

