90 Day	x.xx% [x.xx%-x.xx%]	x.xx% [x.xx%-x.xx%]	x.xx [x.xx-x.xx]	x.xx [x.xx-x.xx]	x.xx [x.xx-x.xx]
1 Year	x.xx% [x.xx%-x.xx%]	x.xx% [x.xx%-x.xx%]	x.xx [x.xx-x.xx]	x.xx [x.xx-x.xx]	x.xx [x.xx-x.xx]
Stroke					
90 Day	x.xx% [x.xx%-x.xx%]	x.xx% [x.xx%-x.xx%]	x.xx [x.xx-x.xx]	x.xx [x.xx-x.xx]	x.xx [x.xx-x.xx]
1 Year	x.xx% [x.xx%-x.xx%]	x.xx% [x.xx%-x.xx%]	x.xx [x.xx-x.xx]	x.xx [x.xx-x.xx]	x.xx [x.xx-x.xx]

Table 4 In and Out of Hospital Post-Procedural Events by Therapy at PCI.

	Clopidogrel	Prasugrel	Unadjusted HR [95% CI]	Propensity adjusted HR [95% CI]	Covariate-adjusted HR [95% CI]
Def/Probable Stent Thrombosis					
90 Day	x.xx% [x.xx%-x.xx%]	x.xx% [x.xx%-x.xx%]	x.xx [x.xx-x.xx]	x.xx [x.xx-x.xx]	x.xx [x.xx-x.xx]
1 Year	x.xx% [x.xx%-x.xx%]	x.xx% [x.xx%-x.xx%]	x.xx [x.xx-x.xx]	x.xx [x.xx-x.xx]	x.xx [x.xx-x.xx]

¹MACE is defined as all cause death, hospitalization for myocardial infarction, stroke, or unplanned revascularization. ²HR calculated from propensity stratified model. ³HR calculated multivariable-adjusted model.

Table 6. Healthcare Utilization and Costs by Therapy at Discharge

	Overall (N = XX)	Prasugrel XX (XX%)	Clopidogrel XX (XX%)	Pvalue
Index Hospital Length of Stay				
N, N Missing	xxx,x	xxx,x	xxx,x	
Mean ± Std	x.xx ± x.xx	x.xx ± x.xx	x.xx ± x.xx	
Median	x.xx	x.xx	x.xx	
Min , Max	x.xx,x.xx	x.xx,x.xx	x.xx,x.xx	
Index Hospital Total Costs				
N, N Missing	xxx,x	xxx,x	xxx,x	
Mean ± Std	x.xx ± x.xx	x.xx ± x.xx	x.xx ± x.xx	
Median	x.xx	x.xx	x.xx	
Min , Max	x.xx,x.xx	x.xx,x.xx	x.xx,x.xx	

Table 6. Healthcare Utilization and Costs by Therapy at Discharge

	Overall (N = XX)	Prasugrel XX (XX%)	Clopidogrel XX (XX%)	Pvalue
30 day Rehospitalization Total Costs				
N, N Missing	xxx,x	xxx,x	xxx,x	
Mean ± Std	x.xx ± x.xx	x.xx ± x.xx	x.xx ± x.xx	
Median	x.xx	x.xx	x.xx	
Min , Max	x.xx,x.xx	x.xx,x.xx	x.xx,x.xx	
90 day Rehospitalization Total Costs				
N, N Missing	xxx,x	xxx,x	xxx,x	
Mean ± Std	x.xx ± x.xx	x.xx ± x.xx	x.xx ± x.xx	
Median	x.xx	x.xx	x.xx	
Min , Max	x.xx,x.xx	x.xx,x.xx	x.xx,x.xx	
180 day Rehospitalization Total Costs				
N, N Missing	xxx,x	xxx,x	xxx,x	
Mean ± Std	x.xx ± x.xx	x.xx ± x.xx	x.xx ± x.xx	
Median	x.xx	x.xx	x.xx	
Min , Max	x.xx,x.xx	x.xx,x.xx	x.xx,x.xx	
1yr Rehospitalization Total Costs				
N, N Missing	xxx,x	xxx,x	xxx,x	
Mean ± Std	x.xx ± x.xx	x.xx ± x.xx	x.xx ± x.xx	
Median	x.xx	x.xx	x.xx	
Min , Max	x.xx,x.xx	x.xx,x.xx	x.xx,x.xx	
1yr Aggregate (Index + Rehospitalization) Total Costs				
N, N Missing	xxx,x	xxx,x	xxx,x	

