Number of acute MI hospitalization within one year of procedure	##	Total number of acute MI hospitalization within one year of index procedure date

Unplanned revascularization within one year of procedure	0=no, 1=yes	Hospitalization for unplanned revascularization with CABG or PCI within one year of index procedure date
Unplanned revascularization date	DDMMYYYY	Date of event
Number of unplanned revascularization hospitalization within one year of procedure	##	Total number of unplanned revascularization hospitalization within one year of index procedure date
Bleeding within one year of procedure	0=no, 1=yes	Hospitalization for bleeding within one year of index procedure date
Bleeding date	DDMMYYYY	Date of event
Number of bleeding hospitalization within one year of procedure	##	Total number of bleeding hospitalizations within one year of index procedure date.
Type of Bleeding	1=access site; 2=GI; 3=GU; 4=CNS; 5=other; 6=unknown	1)Access site 2) GI 3) GU 4) CNS 5) Other 6)Unknown
Stroke within one year of procedure	0=no, 1=yes	Was the patient diagnosed as having a stroke within one year of index procedure date
Stroke date	DDMMYYYY	Date of event
Stroke type	1=ischemic; 2=hemorrhagic; 3=unknown	1) Ischemic 2) Hemorrhagic
Number of stroke hospitalizations within one year of procedure	##	Total number of stroke hospitalizations within one year of index procedure date.
Definite/Probable ST	0=no, 1=yes	Hospitalizations for Definite/Probable Stent Thrombosis
Definite/Probable ST date	DDMMYYYY	Date of Event

last follow up date	DDMMYYYY	Last date of encounter with patient
---------------------	----------	-------------------------------------

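### Index stay, index cost and the index part of one-year cost are grouped by discharge drug, which is set only after they accrue; the direction of the bias is uncertain

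*SAP*

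**What the plan says.** **Clinical exposure.** SAP 6.1 defines the groups by the drug received at PCI: "All patients will be assigned to one of these mutually exclusive groups irrespective of medication administered at discharge".

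**Economic exposure.** The table listing in SAP section 12 titles its Table 5 "Economic Outcomes by Discharge Therapy". The corresponding mock is numbered 6 and headed "Table 6. Healthcare Utilization and Costs by Therapy at Discharge". Its first row is "Index Hospital Length of Stay", followed by index total cost, rehospitalization cost at 30, 90 and 180 days and one year, and a one-year aggregate that adds index and rehospitalization costs.

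**Eligibility.** Protocol 3.3.3 requires discharge on the drug used in the peri-procedural period. SAP 5.3 asks only for treatment before or during that period.

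**Propensity score.** Protocol 3.4.1 describes the score as the chance of having received one drug or the other at discharge, and 3.4.2.2 carries it into the economic weighting. SAP 6.1 models treatment initiation. The SAP's economic methods (6.2) are deferred to Addendum 1, which is not among the documents.

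**Costing.** Protocol 3.4.2.1 assigns DRG payments from the diagnoses of interest and states: "Bleeding-related rehospitalization costs will not be included in this specific analysis". The reason given is that the DRG for such admissions cannot be determined. The diagnoses costed in SAP 7.1 also leave out bleeding, without repeating that reason.

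**The concern.** Length of stay runs from admission to discharge, so it is complete when the discharge prescription is written. A bleed or an ischemic event on the ward can lengthen the stay and also change the drug the patient leaves on. Grouping by discharge drug then sorts patients partly by the outcome being compared. The same holds for index cost where the event changes the assigned DRG, and for the index part of the aggregate.

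Index length of stay is a named economic objective (Protocol 3.2.2), and a separate economic manuscript is planned (Protocol 3.8). Under the SAP a switcher can contribute MACE to one arm and cost to the other, so clinical and economic results would describe different groups. A patient who dies in hospital has no discharge drug, and the visible text does not say where that stay and cost go.

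**Working it through.** The documents give no figure for this bias, so there is none to reproduce. The check compares the passages and then uses an illustration to see which way the bias can run.

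**1. When the groupings differ.** Under Protocol 3.3.3, peri-procedural and discharge drug agree for every eligible patient, so post-procedure switchers are out. Under SAP 5.3 and 6.1 they are in, and the groupings diverge for them.

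**2. The SAP's own precedent.** Sensitivity analysis 5 in SAP 6.1 requires the same drug at PCI and discharge. It therefore limits the outcome to out-of-hospital MACE and excludes in-hospital deaths. Mock Table 6 uses discharge drug without that limit.

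**3. Illustration for stay.** All inputs are assumptions: equal arms at PCI and the same base stay in both (both cancel), bleeding and ischemic events in different patients, and the event rates, added days and switching probabilities shown. Differences are prasugrel minus clopidogrel, in days.

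*Switching after bleeding.* Bleeding share b in each arm, D extra days, and a fraction s of prasugrel bleeders leaving on clopidogrel:

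difference = b(1-s)D/(1-bs) - (b+bs)D/(1+bs)

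- b = 3%, D = 2, s = 25%: 0.0225×2/0.9925 - 0.0375×2/1.0075 = 0.045 - 0.074 = -0.03
- b = 3%, D = 4, s = 75%: 0.0075×4/0.9775 - 0.0525×4/1.0225 = 0.031 - 0.205 = -0.17

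*Switching after ischemic events.* Ischemic share i in each arm with 4 extra days, and a fraction u of clopidogrel patients with such an event leaving on prasugrel. Both arms also have 3% bleeding with 4 extra days and no switching after it:

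difference = 4(0.03+i+iu)/(1+iu) - 4(0.03+i-iu)/(1-iu)

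- i = 1%, u = 25%: 0.170/1.0025 - 0.150/0.9975 = +0.02
- i = 3%, u = 75%: 0.330/1.0225 - 0.150/0.9775 = 0.323 - 0.153 = +0.17

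The true difference is zero in all four cases.

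*Both flows together*, with bleeding 4% on prasugrel and 3% on clopidogrel, and 4 extra days per event:

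| Ischemic share, each arm | s | u | True difference | By discharge drug |
|---|---|---|---|---|
| 2% | 50% | 50% | +0.04 | -0.04 |
| 3% | 25% | 75% | +0.04 | +0.13 |

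The first row reverses the sign and the second roughly triples the difference.

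**4. Index cost.** DRGs come from MI, stroke, unplanned revascularization and stent thrombosis. On that text a bleed lengthens the stay but does not raise the DRG-based index cost. An ischemic event can raise it.

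**5. Omitted bleeding cost.** Per-patient difference = (prasugrel rate - clopidogrel rate) × payment, with an assumed payment of $6,000 to $12,000:

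- 3% against 2%: $60 to $120
- equal rates: $0
- 1.8% against 2%: -$12 to -$24

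**The case against.** Four arguments weigh against the concern.

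- *Protocol eligibility removes the problem.* That is true of the protocol's population, but not of the SAP's, which the mock tables serve.
- *Addendum 1 may settle it.* It may. The table titles in the SAP body nevertheless name discharge drug already.
- *Most rows of mock Table 6 are post-discharge costs on a discharge clock.* This stands. The timing fault does not reach them, nor the hypothesis on 30-day resource use in Protocol 3.2.3.
- *The bleeding omission is disclosed, and bleeding readmissions are still compared as rates (Protocol 3.2.2).* This also stands, so the omission calls for labeling and a sensitivity analysis. The type field, "1=access site; 2=GI; 3=GU; 4=CNS; 5=other; 6=unknown", gives site without severity and is recorded once even when a patient has several bleeding admissions.

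A reader might go further and infer that the grouping and the omission both tilt toward prasugrel. The documents do not support that. The grouping bias changes sign with the dominant switch. On bleeding, the SAP background reports that in a randomized trial "prasugrel caused higher rates of major bleeding", but it also cites a claims study with no significant adjusted difference in bleeding rehospitalization. A reader might also infer that the economic propensity score models the wrong exposure. The protocol's version matches discharge drug and the SAP's matches initiation; which one applies to the economic tables is unsettled, so a mismatch is not shown.

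**Conclusion.** The point holds for three rows: index length of stay, index total cost and the index part of one-year aggregate cost. Under the SAP's population they are compared across groups that form only after the outcome has accrued and that can depend on it. Switchers may change arms between clinical and economic results, and in-hospital deaths have no economic group.

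The direction is uncertain. Switching after bleeding favors prasugrel on stay; switching after ischemic events goes the other way. The spurious difference of about -0.17 to +0.17 days rests wholly on assumed event rates (1 to 3%), added days (2 to 4) and switching (25 to 75%). The documents give no in-hospital switching rate; their expectations on switching (10% or less, and under 15%) concern the 90-day period.

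Leaving out bleeding payments favors prasugrel only if its bleeding readmissions are more frequent or costlier. That is plausible but not established.

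**What to change.** 1. Group index length of stay, index cost and aggregate cost by therapy at PCI, using the primary analysis groups and a propensity score for drug at PCI. Keep in-hospital deaths.
2. Use discharge-drug grouping only as a sensitivity analysis of post-discharge outcomes, with the clock at discharge and a score that models discharge drug. State which score serves which table, reconciling Protocol 3.4.1 and 3.4.2.2 with SAP 6.1.
3. Correct the Table 2 mock title, which says discharge therapy where the listing says therapy at PCI, and align the economic table's number (5 in the listing, 6 in the mock).
4. Label cost totals as excluding bleeding readmissions. As a sensitivity analysis only, show totals with an approximate payment by recorded bleeding type and an average for other or unknown.

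The cost is a change of grouping variable, table titles, a short text in Addendum 1 and a small payment lookup. No new patient data are needed. The downside is that the bleeding payments would be approximate.
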